7.2 DISPOSITION OF SUBJECTS

The enrolled population will be represented in the disposition table. The disposition table will be broken down by diagnosis (AD, MCI, CN and SMC) and include a summary of the analysis populations, number of completed and discontinued subjects, and the reasons for discontinuation.

Disposition data will be presented in a listing.

7.3 ANALYSIS OF SCREENING AND BASELINE ASSESSMENTS

7.3.1 *Demographic and Other Baseline Characteristics*

All baseline summaries will be based on the safety population. Age (years), gender, amyloid status (A β +, A β -), tau status (AD-, AD+, AD++), race, ethnicity, height (cm), weight (kg), BMI, years of education, substance use (alcohol, smoking, and recreational drug history), MMSE, CDR-SB will all be reported in the demographics table using descriptive statistics.

All baseline cognitive scores are collected in the AIBL database. Baseline height and weight are the measurements collected on the AV-1451-A08 CRF.

7.3.2 *Medical and Surgical History*

Medical and surgical histories were coded using MedDRA version 17.0. Medical and surgical history will be defined in the same manner as in the protocol. Medical and surgical history will be presented for the safety population in a listing.

7.3.3 *Concomitant Therapy*

Concomitant therapies were coded using WHODRUG V20140601. Concomitant medications are medications that started prior to, on or after the informed consent date and ended on or after the date of the flortaucipir injection or were ongoing at the end of the study. Concomitant medications will be presented for the safety population in a listing.

7.3.4 *Physical Examination*

Physical examination will be summarized for the safety population. Each assessment of the physical examination – general appearance, skin, HEENT, respiratory, cardiovascular, gastrointestinal, musculoskeletal – will be summarized in a table in aggregate and by diagnosis.

Individual subject assessments will be presented in a listing, including any abnormalities noted on the CRF.

7.3.5 Neurological Examination

Neurological examination will be summarized using the safety population. Each assessment of the neurological examination – level of consciousness, mood and affect, cranial nerves, motor function, fundoscopy, sensory function, gait cerebellar, reflexes – will be summarized in a table in aggregate and by diagnosis.

Individual subject assessments will be presented in a listing, including any abnormalities noted on the CRF.

7.3.6 History of Cognitive Decline

History of cognitive decline will be presented in a listing for the safety population.

7.3.7 Family History of Dementing Disorder

Family history of dementing disorders will be presented in a listing for the safety population.

7.3.8 Electrocardiogram (ECG)

ECG data captured on the CRF will be presented in a listing for the safety population.

7.3.9 Safety Labs

Safety Lab data captured on the CRF will be presented in a listing for the safety population.

7.3.10 MRI Visit

MRI data captured on the CRF will be presented in a listing for the safety population.

7.4 ANALYSIS OF EFFICACY PARAMETERS

7.4.1 Primary Efficacy Analysis

The primary analysis will be analyzed in both the quantitative (MUBADA SUVR) and qualitative (the visual interpretation of the baseline flortaucipir scan) measures of brain flortaucipir accumulation.

7.4.1.1 Two-way Analysis of Variance for Comparison of MUBADA SUVR across Cognitive Groups

The first hypothesis for testing is whether MUBADA SUVr is the same or different between subjects with objective cognitive impairment (AD and MCI) and subjects without objective cognitive impairment (CN and SMC) at baseline.

The second hypothesis for testing is whether MUBADA SUVr is the same or differs between subjects with objective cognitive impairment (AD and MCI) and SMC subjects at baseline.

The third hypothesis for testing is whether MUBADA SUVr is the same or differs between SMC and CN subjects at baseline.

Depending on available data, a two-way analysis of variance (ANOVA) model will be used to test all three hypotheses. Baseline MUBADA SUVr will be the dependent variable, with cognitive group (AD, MCI, CN and SMC) and amyloid status (A β + and A β -) as the fixed effects. The appropriate contrast will be set up to test each hypothesis.

Descriptive summary statistics along with least squares means (LSM) for SUVr at baseline will be summarized for all subjects by cognitive group (AD, MCI, SMC, CN). The difference in LSM between groups and p-values from each ANOVA contrast will be included in the table.

Box-and-whisker plots will be generated to visualize SUVr distribution across cognitive groups.

7.4.1.2 Relationship of Qualitative Flortaucipir Uptake and Cognitive Status

The first hypothesis will test whether a relationship exists between the subjects who exhibit an AD pattern likely to progress and those who do not (AD++ vs. Non-AD++), as determined by the visual interpretation of the baseline flortaucipir scan, and cognitive status (AD, MCI, CN, SMC), while controlling for amyloid status.

The second hypothesis will test whether a relationship exists between all subjects with an AD pattern (AD+ and AD++ vs. AD-), and cognitive status, while controlling for amyloid.

Depending on available data, Cochran Mantel Haenszel's (CMH) test for general association will be used to test both of these hypotheses. Further, Pearson's chi-square test of association will be used to test this hypothesis within each amyloid group separately. Fisher's exact test will be used in the event that at least one expected cell count is less than 5. The joint distributions (frequency and percentages) from each amyloid group, along with the p-values from the CMH and Pearson chi-square (or Fisher's exact) tests from each hypothesis will be summarized in a unique table.

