## 8.4 Primary objective analysis

Descriptive statistics will be applied to summarize the tau deposition as measured by F-AV-1451 uptake values by clinical enrollment groups. Box-and-Whiskers plots by clinical enrollment groups will be created to describe the tau deposition

distributions. ANOVA test will be applied to compare the tau deposition between subjects with objective cognitive impairment (MCI and AD) and subjects without objective cognitive impairment (healthy controls and subjects with SMC) at baseline, and at 12 months follow up visit. If the pre-requisites of ANOVA are not met then appropriate non parametric test such as Kruskal-Wallis test will be applied.

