2 STUDY OBJECTIVES

The primary objective of this study is:

- To compare the density and distribution of flortaucipir uptake among men and women aged over 60 years with objective cognitive impairment (MCI and AD) and without objective cognitive impairment (CN and subjects with SMC).

The exploratory objectives of this study are:

- To determine the prevalence and distribution of brain tau in men and women aged over 60 years with and without subjective cognitive complaints.
- To relate the regional distribution of brain tau deposits to the presence of brain amyloid, current cognitive and brain function as well as brain atrophy.
- To relate the change over time in the levels of regional brain tau to baseline brain tau, baseline brain amyloid and change over time in cognition and function, and brain volume.
- To expand the flortaucipir safety database.

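### The visual-read half of the primary analysis gives no test, estimate or interval for the impaired-versus-unimpaired comparison that is the SAP's primary objective

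*SAP*

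**What the plan says.** SAP section 2 sets the primary objective as a comparison of flortaucipir uptake between people over 60 "with objective cognitive impairment (MCI and AD) and without objective cognitive impairment (CN and subjects with SMC"). Protocol 8.4 names the same two sides: its ANOVA is to "compare the tau deposition between subjects with objective cognitive impairment (MCI and AD) and subjects without objective cognitive impairment".

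SAP 7.4.1 gives the primary analysis two measures: "The primary analysis will be analyzed in both the quantitative (MUBADA SUVR) and qualitative (the visual interpretation of the baseline flortaucipir scan) measures".

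- **SUVr (SAP 7.4.1.1).** The first hypothesis is AD and MCI against CN and SMC. It is tested in a two-way ANOVA with amyloid status as the other factor, and "The appropriate contrast will be set up to test each hypothesis". The table carries the difference in least squares means and the p-value.
- **Visual read (SAP 7.4.1.2).** The first hypothesis relates AD++ versus non-AD++ to "cognitive status (AD, MCI, CN, SMC), while controlling for amyloid status". The second concerns "all subjects with an AD pattern (AD+ and AD++ vs. AD-), and cognitive status", again controlling for amyloid. The CMH "test for general association will be used to test both of these hypotheses". Pearson or Fisher tests follow within each amyloid group. The output is joint frequencies and percentages by amyloid group, with p-values.

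For the visual read, the SAP plans no pooled impaired-versus-unimpaired test, contrast, odds ratio, risk difference or confidence interval.

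**The concern.** One primary objective is examined with two primary measures, and only one of them addresses the comparison that the objective names. The visual-read test asks whether the four diagnoses differ in any way at all. A small p-value could come from AD against MCI, from SMC against CN, from impaired against unimpaired, or from a mixture. A large one leaves the reader with no interval to show which impaired-versus-unimpaired differences remain compatible with the data. In either case the report could not say from this analysis how much more often an AD++ read (or any AD pattern) occurs in impaired subjects at a given amyloid status.

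**Working it through.** The plan states no power or sample-size figure to reproduce. SAP 3.3 says that the size was set without statistical consideration.

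**Inputs from the documents.** Planned groups (protocol synopsis): CN 25, SMC amyloid-negative 25, SMC amyloid-positive 25, MCI 25, AD 20; 25+25+25+25+20 = 120. Alpha is 0.05 two-sided with no multiplicity adjustment (SAP 6.11).

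**Assumptions, not in the documents.** The amyloid splits of CN, MCI and AD, and all AD++ rates.

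**1. Degrees of freedom.** For CMH general association, df = (rows − 1)(columns − 1) = (4 − 1)(2 − 1) = 3 for each hypothesis. Collapsed to impaired versus unimpaired, df = (2 − 1)(2 − 1) = 1.

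**2. Power at equal noncentrality.** This is the case in which the whole signal lies between the two sides. Noncentrality is λ = (z₀.₉₇₅ + z_power)².
- 80% with 1 df: λ = (1.960 + 0.842)² = 7.85. The same λ on 3 df gives 64.5%.
- 90% with 1 df: λ = 10.51. The same λ on 3 df gives 78.4%.
- For 80% power, the 3-df test needs 1.39 times the sample size. Conversely, the 1-df test is the stronger one at that level only if the two-sided contrast carries more than 1/1.39 = 72% of the total noncentrality.

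**3. Simulated power.** Each scenario has 4,000 runs, stratified by amyloid. Amyloid-positive counts for CN/SMC/MCI/AD are 6/25/16/18 (mix 1) or 12/25/20/20 (mix 2). The AD++ rate is 2% in amyloid-negatives; in amyloid-positives it is as listed.

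| AD++ rate, CN/SMC/MCI/AD | Mix 1: 3 df vs 1 df | Mix 2: 3 df vs 1 df |
|---|---|---|
| 15/15/45/45% (alike within sides) | 55% vs 74% | 67% vs 84% |
| 10/10/40/40% (alike within sides) | 62% vs 82% | 72% vs 88% |
| 10/10/30/60% (graded) | 90% vs 92% | 94% vs 95% |
| 5/10/30/70% (graded) | 99% vs 98% | near 100% vs 99% |
| 15/15/15/50% (AD alone raised) | 66% vs 39% | 74% vs 43% |

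A second set uses odds ratios against the unimpaired. Amyloid-positive counts for CN/SMC/MCI/AD are 6/25/17/18, and unimpaired AD++ rates are 20% (amyloid-positive) and 4% (amyloid-negative). Power, 3 df vs 1 df:
- AD and MCI both at 4: 65% vs 80%
- AD 6, MCI 3: 74% vs 84%
- AD 6, MCI 2: 71% vs 71%
- AD alone at 5: 68% vs 39%

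**4. Rejection with the two sides about equal.** These scenarios are constructed to show what the p-value can and cannot mean. Rates are for amyloid-positives.
- CN 0%, SMC 40%, MCI and AD 32%. In mix 1 the unimpaired side pools to 0.40 × 25/31 = 32%, equal to the impaired side; in mix 2 it pools to 0.40 × 25/37 = 27%. The 3-df test rejects in 14% (mix 1) and 50% (mix 2) of runs; the 1-df test in 4% and 7%.
- MCI 0%, AD 60%, CN and SMC 32%. The impaired side pools to 0.60 × 18/34 = 32% (mix 1) or 0.60 × 20/40 = 30% (mix 2). The 3-df test rejects in 97% and nearly 100% of runs; the 1-df test in 3% and 4%.

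**The case against.** General association is the right test for the hypothesis that 7.4.1.2 states, namely a relationship with four-level cognitive status; the issue is which hypothesis to state. Protocol 8.4 concerns uptake values only. SAP 4.2 records the visual reads as an addition, so the protocol prescribes no two-group test of them. SMC against CN is itself the third SUVr hypothesis in 7.4.1.1, so a result driven by that pair is not foreign to the primary analysis. The planned percentages by amyloid group let a reader see the direction and work out a pooled odds ratio by hand. The SUVr half tests the objective directly, and the study is exploratory with no power target to miss.

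All of this stands, and it limits the impact. It does not supply what is missing: a pre-specified test, estimate and interval for the objective's comparison in a measure that the SAP itself calls primary.

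A reader might go further and infer that the four-group test is simply underpowered. The documents do not support that. They give no AD++ rates, and the protocol Introduction describes tau as rising with impairment, which points to a gradient; in the graded scenarios above, the difference ranges from 10 points lower to slightly higher. Nor should the constructed scenarios in step 4 be read as likely. The first puts SMC above the impaired groups, and the second puts MCI below the unimpaired; both run against that gradient.

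**Conclusion.** The mismatch is established from the text and holds whatever the read rates are. The fault is one of interpretation: a 3-df p-value without direction, with no effect estimate or interval for the comparison in the objective. Power is a conditional matter. The planned test loses roughly 15 to 20 points if rates are alike within each side, is about equal or moderately lower under a gradient, and gains more than 25 points if AD alone is raised. These power figures rest on assumed AD++ rates and amyloid splits. They justify adding the direct comparison; they do not justify dropping the four-group test.

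**What to change.** In SAP 7.4.1.2, add a 1-df CMH test of AD+MCI versus CN+SMC, stratified by amyloid status, and name it as the visual-read test of the primary objective. Do this for both dichotomies: AD++ versus non-AD++, and AD+ or AD++ versus AD-. Report the Mantel-Haenszel common odds ratio or risk difference, chosen in advance, with a 95% CI. Keep the four-group general-association test, the within-amyloid tests and the frequency tables for differences among the individual diagnoses.

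The cost is SAP wording, one more table row per hypothesis and one more unadjusted p-value per hypothesis; no new data are needed. The added test is the weaker of the two if only AD is raised (39% against 66% in mix 1), which is why the four-group test should stay.

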7.4.2 Exploratory Analysis

All exploratory analysis involving flortaucipir quantitation will be run with MUBADA SUVr only.

7.4.2.1 Two-way ANOVA for Comparison of MUBADA SUVr between Amyloid Groups

Depending on available data, the same analyses as described in Section 7.4.1.1 will be performed with the substitution of comparing MUBADA SUVr between amyloid groups (A β + vs. A β -) rather than cognitive groups, via properly set up contrasts.

7.4.2.2 ANCOVA for Comparison of MMSE CFB as a Function of Tau Scan Visual Interpretation

The objective of this analysis is to determine if baseline tau status will predict subjects' cognitive deterioration.

The first hypothesis will test whether a difference in MMSE CFB exists between AD++ and Non-AD++ (AD- and AD+ only) subjects at 12 month follow-up visit.

The second hypothesis will test whether a difference in MMSE CFB exists between subjects with AD pattern (AD+ and AD++) and AD- subjects.

The third hypothesis will test whether a difference in MMSE CFB exists between AD++ and AD- subjects.

Depending on available data, an ANCOVA model with MMSE CFB at 12 months as the dependent variable, adjusted for baseline MMSE, age, cognitive group, level of education, and the interaction of cognitive group and tau status will be used to test these hypotheses. The appropriate contrasts will be set up to test each hypothesis.

Descriptive summary statistics for MMSE at baseline, 12 months and CFB will be summarized for all subjects by tau status (AD-, AD+, AD++). Group LSM, the difference in LSM between groups, and the p-values from each ANCOVA contrast will be included in the table.

A scatter plot will be created to display the relationship between MMSE CFB and baseline MUBADA SUVr across each tau group.

7.4.2.3 ANCOVA for Comparison of CDR-SB CFB as a Function of Tau Scan Visual Interpretation

The same analyses as described in Section 7.4.2.2 will be performed with the substitution of CDR-SB for MMSE.

7.4.2.4 ANCOVA for Comparison of MMSE CFB as a Function of Cognitive Status

This analysis will test the hypothesis whether there is a difference between subjects with objective cognitive impairment (AD and MCI) and SMC subjects. The same analyses as described in Section 7.4.2.2 will be performed with the substitution of impairment group (AD and MCI vs. SMC) for tau status, via properly set up contrasts.

7.4.2.5 ANCOVA for Comparison of CDR-SB CFB as a Function of Cognitive Status

The same analyses as described in Section 7.4.2.4 will be performed with the substitution of CDR-SB for MMSE.

7.4.2.6 Risk Ratio of AD++ vs. Non-AD++ Subjects in Progression to Clinically Meaningful Changes Evaluated by MMSE

The specific hypothesis for testing is the risk of progressing to a clinically meaningful event (≤ -3 change) as determined by MMSE value change within 12 months will be significantly greater for subjects in the AD++ group as compared to those in the non-AD++ group (otherwise, including AD- and AD+ only but not AD++ reading).

As described in section 5.2.5.3, the MMSE CFB will be the dichotomized (3 point or more decrease vs. otherwise). Depending on available data, incidence of this clinically meaningful event by tau visual read groups will be compared using a log-linear model adjusted for baseline age, years of education, and baseline MMSE score. The Poisson distribution will be chosen for the dependent variable and a log link function will be used to model for the risk ratio.

The risk ratio of AD++ rated subjects progressing to the event over non-AD++ rated subjects along with the 95% confidence interval will be provided.

7.4.2.7 Risk Ratio of AD++ vs. Non-AD++ Subjects in Progression to Clinically Meaningful Changes Evaluated by CDR-SB

The same analyses as described in Section 7.4.2.6 will be performed with the substitution of CDR-SB clinically meaningful progression (≥ 1 point change) for MMSE clinically meaningful progression.

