5.2.5.3 Clinically Meaningful Progress

The MMSE and CDR-SB assessments will be dichotomized, to allow for the assessment of risk to progress to a clinically significant change. Subjects will be categorized to these groups by the criteria accordingly.

- MMSE: clinically significant progress is defined as MMSE has a 3 points or more decrease from baseline.
- CDR-SB: clinically significant progress is defined as CDR-SB has a 1 point or more increase from baseline.

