6.8 ADJUSTMENTS FOR COVARIATES

Analysis of Covariance (ANCOVA) models evaluating cognitive change in the exploratory analyses will be adjusted for the baseline value of the cognitive score, age, and years of education. Log-linear models estimating risk ratios in the exploratory analyses will be adjusted for the baseline value of the cognitive score, age, and years of education. ANCOVA models evaluating SUVr CFB in the exploratory analysis will be adjusted for baseline SUVr and age.

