6.11 MULTIPLE COMPARISONS/MULTIPLICITY

No multiple comparisons/multiplicity adjustment is planned. Unless otherwise specified, hypothesis testing will be two-sided with type I error rate of 0.05.

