7.1.3 Efficacy Population

The efficacy population used in the primary analysis will include all subjects in the safety population with a valid interpretable baseline PET image (SUVr and/or visual read) available. The exploratory efficacy population will include all subjects with available SUVr, flortaucipir visual read, and the relevant clinical/cognitive assessment.

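### The two exploratory risk-ratio analyses fit a Poisson model to a yes/no outcome without naming a robust variance, so the 95% CI that the model implies is too wide on average

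*SAP*

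**What the plan says.** SAP 5.2.5.3 turns each cognitive score into a yes/no result: "The MMSE and CDR-SB assessments will be dichotomized, to allow for the assessment of risk to progress to a clinically significant change". Progression is a fall of at least 3 points on the MMSE, or a rise of at least 1 point on the CDR-SB.

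SAP 7.4.2.6 models the MMSE result: "The Poisson distribution will be chosen for the dependent variable and a log link function will be used to model for the risk ratio". The listed output is a ratio and an interval: "The risk ratio of AD++ rated subjects progressing to the event over non-AD++ rated subjects along with the 95% confidence interval will be provided". No p-value is listed, but the hypothesis says that the risk "will be significantly greater for subjects in the AD++ group as compared to those in the non-AD++ group", and SAP 6.11 adds that "hypothesis testing will be two-sided with type I error rate of 0.05". A test is therefore implied. SAP 7.4.2.7 applies the same method to CDR-SB.

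On adjustment, SAP 6.8 says: "Log-linear models estimating risk ratios in the exploratory analyses will be adjusted for the baseline value of the cognitive score", and adds age and years of education. No variance estimator appears in SAP 6.1, 6.8, 6.9, 6.11, 7.4.2.6 or 7.4.2.7.

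**The concern.** A Poisson variable with mean p has variance p. A yes/no variable with mean p has variance p(1-p), which is smaller. A Poisson log-link fit to yes/no data is a recognised way to obtain a risk ratio, and its point estimate is sound. The standard error taken from the Poisson likelihood is not, unless the risks are small. A programmer who follows the text and takes the software's default variance will report an interval that is too wide on average.

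The stake is sensitivity. SAP 7.4.2.6 expects a higher risk in AD++ subjects, and the study size was not based on any power calculation (SAP 3.3). An over-wide interval works against detecting that difference.

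**Working it through.** **Inputs.** From the documents: about 120 subjects planned, of whom 25 + 25 + 25 = 75 have no objective impairment (Protocol synopsis); covariates as in SAP 6.8; two-sided 0.05 (SAP 6.11). The documents give no AD++ count, event risk, risk ratio or power for this analysis, so there is no figure of the plan's own to reproduce. Assumed: 110 subjects analysed, split 30/80 or 15/95 (AD++/non-AD++), with a range of risks.

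**Closed form, unadjusted.** With a events among n1 AD++ subjects and c events among n0 non-AD++ subjects:

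- Poisson, model-based: Var(log RR) = 1/a + 1/c
- Yes/no outcome: Var(log RR) = 1/a - 1/n1 + 1/c - 1/n0

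Example, 30/80 at 30% vs 10%: a = 9, c = 8.

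- Poisson: 1/9 + 1/8 = 0.2361, SE 0.486
- Yes/no: 0.2361 - 1/30 - 1/80 = 0.1903, SE 0.436
- Ratio: 0.486/0.436 = 1.114

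| AD++ vs non-AD++ risk | SE ratio, 30/80 | SE ratio, 15/95 |
|---|---|---|
| 10% vs 3% | 1.032 | 1.040 |
| 20% vs 5% | 1.060 | 1.080 |
| 30% vs 10% | 1.114 | 1.144 |
| 50% vs 10% | 1.146 | 1.216 |
| 50% vs 20% | 1.245 | 1.308 |
| 50% vs 25% | 1.283 | 1.336 |

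The last two rows need a 20-25% one-year risk among non-AD++ subjects. That is demanding when 75 of 120 planned subjects have no objective impairment; the documents neither support nor exclude it.

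**Adjusted model, simulated.** Read group plus three covariates, 8,000 datasets per scenario, HC1 as the robust variance.

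- Power at 30/80, 30% vs 10%: 62.3% model-based against 68.7% robust when the covariates are unrelated to outcome. With one covariate related to outcome it is 62.3% against 70.7%.
- Rejection with no true difference at 30/80: 1.9% against 2.9% at 10% risk, and 1.6% against 4.2% at 30% risk (nominal 5%).
- Share of the gap to 5% that the variance choice explains: (2.9 - 1.9)/(5 - 1.9) = 1.0/3.1, about one third, at 10% risk; (4.2 - 1.6)/(5 - 1.6) = 2.6/3.4, about three quarters, at 30% risk. The rest is sparse data, which a robust variance does not cure.

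A separate simulation (110 subjects, 30% AD++, robust variance without the small-sample factor, 1,000 datasets per scenario) gave model-based coverage of 97.2-98.6% and robust coverage of 93.5-97.2%.

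**Direction in single datasets.** In that second simulation the robust SE exceeded the model-based SE in up to 27% of fits (20% vs 2% risk). The excess width is an average property.

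**Very few events.** At 15/95 with 5% risk in both groups, the chance of no AD++ event is 0.95^15 = 0.46, and 46% of fits were unusable. Among usable fits the robust test rejected about 7-9% of the time, against 4.3% model-based.

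**The case against.** The strongest reply is that SAP 7.4.2.6 names a distribution and a link and is silent on variance. A sandwich variance is compatible with that text, so nothing stated is wrong, and the analyses are exploratory and unpowered. Part of this stands. A reader might infer that the reported intervals will certainly be too wide; the documents do not support that, because they do not exclude a robust variance. The point concerns the interval that follows from the distribution as written. It is still more than a missing detail, since the only variance the text implies is the wrong one for this outcome.

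A second reply is that the effect is small when events are uncommon. That also stands: the excess is 3-8% at the low-risk settings.

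A third tempting reading is that the missing rule for few events also widens the interval. It does not. SAP 7.4.1.2 has such a rule for its own tables (an "exact test will be used in the event that at least one expected cell count is less than 5"), and 7.4.2.6 offers only a general condition about available data. That is a separate gap: with no events in one group the ratio cannot be estimated. Such data are plausible, because SAP 7.1.3 restricts the set ("The exploratory efficacy population will include all subjects with available SUVr, flortaucipir visual read, and the relevant clinical/cognitive assessment") and SAP 6.9 imputes nothing.

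**Conclusion.** The point holds and is minor. As written, the model gives a valid risk ratio with a 95% CI that is too wide on average and a conservative two-sided 0.05 test. Under the assumed splits and risks, the excess in the standard error runs from about 3% to 34%, and the upper end requires a non-AD++ risk of 20-25%. At 30% vs 10% with 30/80, the cost is about 6 to 8 points of power.

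A reader might go further and say that the choice can hide an association but never create one. That is too absolute, because in sparse adjusted fits the robust standard error can be the larger of the two. Nor is the risk-ratio estimate or any primary analysis affected; the point is confined to SAP 7.4.2.6 and 7.4.2.7. The algebra is certain. The size in this trial is not, because the documents give neither the AD++ count nor the event risks.

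**What to change.** Keep the Poisson log-link model. In both 7.4.2.6 and 7.4.2.7, state that the CI and any p-value use the robust (sandwich) variance with a small-sample factor such as HC1. With 110 subjects and 5 parameters, HC1 multiplies the SE by the square root of 110/105, which is 1.024. The cost is one sentence per section and a few lines of code.

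The downside is that with very few events the robust variance is anti-conservative, as the 15/95 setting at 5% risk shows. The report should therefore give event counts by tau-read group and mark the interval as unreliable when events are very few. A rule for zero or few events is worth adding for its own sake; the trigger and the fallback are for the sponsor to choose, and this point does not depend on any particular one.
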